3. TREATMENT ALLOCATION, RANDOMIZATION AND BLINDING

Upon qualifying for treatment, subjects will be randomized for the side of mouth and the order of injection of study devices (i.e., left or right / 1st or 2nd order). If needed to improve cosmetic results, the lower perioral quadrant of a side will be injected only after both upper perioral quadrants have been injected.

[REDACTED]

[REDACTED]

4. DEVICE APPLICATION

4.1 Injection of Study Devices

[REDACTED]

[REDACTED]

[REDACTED]

[REDACTED]

[REDACTED]

[REDACTED]

4.1.3 Injection Sequence

Upon qualifying for treatment, subjects will be randomized for the side of mouth and the order of injection (i.e., left or right / 1st or 2nd order). Both upper perioral rhytids will be injected prior to injection of either lower perioral rhytid. [REDACTED]

[REDACTED]

[REDACTED]

5.2 Safety

Safety will be evaluated through a 30-day patient Common Treatment Response (CTR) diary that captures post-injection signs/symptoms and AE reporting based on phone follow-ups and clinic visits. [REDACTED]

5.2.1 30-Day Patient Common Treatment Response Diary

The subject will receive a diary booklet and instructions for recording his/her observations of the CTRs of the study treatments for the first 30 days after treatment.

The subject diary will capture the following CTRs that typically occur following the injection of a dermal filler; specifically, redness, pain, tenderness, firmness, swelling, lumps/bumps, bruising, itching, discoloration, and “other”. Subjects will record the presence and the severity of each observed sign/symptom as: none, mild, moderate, or severe.

[REDACTED]

6.4.2 Per Protocol (PP) Population

[REDACTED]

[REDACTED]

6.4.3 Safety (SAFT) Population

[REDACTED]

[REDACTED]

[REDACTED]

[REDACTED]

[REDACTED]

6.6 General Considerations

Data will be listed by treatment group and subject number. The safety and efficacy data will be summarized by treatment allocation. Descriptive statistics will consist of mean, standard deviation, minimum and maximum for continuous variables, and frequency and percent for discrete variables.

This SAP will be finalized and approved by the study Sponsor prior to the last subject's last visit. All programs for data output and analyses will be written in SAS version 9.4 or higher (SAS Institute, Inc., Cary, NC).

[REDACTED]

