6 TREATMENT ALLOCATION, RANDOMIZATION AND BLINDING

All subjects who have signed an ICF will receive a 3-digit subject number, starting at 001. Subject numbers will be assigned in ascending order and will be coupled with the site identification number for unique identification of each subject. The subject number will be used to identify the subject throughout the study. Subjects withdrawn from the study will retain their subject number; new subjects will be allocated a new subject number.

Upon qualifying for treatment, subjects will be randomized for the side of mouth and the order of injection of study devices [REDACTED]. If needed to improve cosmetic results, the lower perioral quadrant of a side will be injected only after both upper perioral quadrants have been injected.

Subjects will be considered “enrolled” at the time of consent, and will be considered “enrolled and randomized” at the time of randomization. The required sample size is based on “enrolled and randomized” subjects. If an enrolled subject withdraws from the study prior to being randomized, he/she may be replaced.

This is a double-blinded study in which subjects and TIs will be blinded to treatment allocation.

Designated site personnel will secure the randomization/treatment allocation information and any other record of study treatment from potential discovery by the TI or the subject. Any instance where the blind is opened to the TI or subject will be documented in writing.

If it is medically imperative to know what device was injected into the left and right perioral rhytids, the TI or study coordinator will contact [REDACTED] to confirm the rationale for unblinding. If appropriate, [REDACTED] and/or the Sponsor will approve unblinding and treatment assignments for that particular subject will be disclosed. The rationale for breaking the code must be recorded in subjects’ medical record and eCRF.

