7.2 Injection of Study Devices

At Visit 1, each enrolled and randomized subject will receive injections of RHA® [REDACTED] with [REDACTED] into the perioral rhytids of the upper left quadrant or the upper right quadrant, and injections of the control device (i.e., RHA® [REDACTED] with lidocaine) into the contralateral upper quadrant. Using the same device as the upper quadrant for that side, the lower perioral quadrant of a side will be injected only after both upper perioral quadrants have been injected and only if needed.

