10.2 Withdrawal

A subject **will be** withdrawn from the study for any of the following reasons:

- Lost to follow-up;
- Withdrawal of consent;
- The Principal Investigator believes that for safety reasons (e.g., AE, concurrent illness) that it is in the best interests of the subject to be withdrawn from study participation;
- The subject's attending physician requests that the subject be withdrawn from the study;
- The Principal Investigator or the Sponsor, for any reason, stops the study or stops the subject's participation in the study.

Protocol deviations will not lead to automatic withdrawal unless they indicate a significant risk to the subject's safety. All major protocol deviations must be discussed promptly with the Medical Monitor.

A subject **may be** withdrawn from the study, in consultation with the Medical Monitor, for any of the following reasons:

[figure not shown]
- Lack of compliance to study procedures;
- A significant protocol deviation or violation;
- Poor visit attendance.

Should a subject decide to withdraw after administration of a study device(s), or should the Principal Investigator decide to withdraw the subject, the Principal Investigator (or designate) will complete and report the observations up to the time of withdrawal.

All subjects who are withdrawn from the study will be requested to come in to complete their next scheduled clinic visit. The next scheduled visit may be brought forward to facilitate this. A complete evaluation at the time of the subject's withdrawal should be made. Additionally, subjects who withdraw from the study will be requested to allow continued safety monitoring, either via telephone interviews or clinic visits, whichever is more appropriate.

The reason and date of withdrawal must be noted on the eCRF. If the reason for withdrawal is an AE or an abnormal laboratory test result, monitoring will continue until resolution or until an appropriate medical judgment concerning the cause or importance has been made. The specific event or test result(s) must be recorded on the eCRF.

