6.8 Safety Analysis

The SAFT Population will be used to summarize the safety of the study devices and will consist of all treated subjects. The primary safety analysis is the calculation of the incidence of CTRs and adverse events in the study period. Point estimates for all CTRs, AEs and SAEs will be presented and two-sided exact 95% confidence intervals will be calculated for the overall incidence of AEs and SAEs. Tables will be generated which summarize AEs by investigator assessments of both relationship to treatment and severity.

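### SAP 6.6 groups safety data by allocated device; side-specific safety should be grouped by the device actually injected, or 6.6 aligned with 6.4.3 if that already says so

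*SAP*

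**What the plan says.** - **Grouping rule.** SAP 6.6 states: "The safety and efficacy data will be summarized by treatment allocation". It makes no exception for safety.
- **Safety set.** SAP 6.8 says: "The SAFT Population will be used to summarize the safety of the study devices and will consist of all treated subjects". Protocol 11.8 has the same text. Membership is decided per subject, not per side or per device received.
- **Meaning of allocation.** Protocol section 6 treats it as the randomised assignment to be concealed: "Designated site personnel will secure the randomization/treatment allocation information and any other record of study treatment from potential discovery by the TI or the subject". SAP section 3 says what is assigned: "subjects will be randomized for the side of mouth and the order of injection of study devices (i.e., left or right / 1st or 2nd order", so side and order are separate factors.
- **Design.** Under Protocol 7.2 the new device goes "into the perioral rhytids of the upper left quadrant or the upper right quadrant, and injections of the control device" into the contralateral upper quadrant. Each subject should therefore contribute one side to each device.
- **Partial treatment.** The withdrawal rule in Protocol 10.2 begins "Should a subject decide to withdraw after administration of a study device(s" (the bracket closes just after the excerpt). The optional plural leaves room for a subject who received only one device.
- **What cannot be read.** Under the heading "6.4.3 Safety (SAFT) Population" the SAP body is blacked out. Protocol 11.4.3 is in the table of contents, but its text is not readable.
- **Precedence.** SAP section 1 makes the SAP prevail over the protocol where they differ.

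**The concern.** Grouping by allocation is a sound default for the efficacy comparison. For local safety, the question is which product was in the tissue that reacted. In a split-face trial that is settled side by side, and two departures from plan would separate the allocated from the injected device:

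1. The two devices are exchanged between sides. Each side's CTRs and local AEs are then reported under a device that was not injected there.
2. Only one device is given. The subject counts as treated, so the device not given keeps a side that had no exposure.

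Both gels are described as clear and colourless with the same hyaluronic acid concentration (Protocol 7.1), and the injector is blinded. An exchange might therefore go unnoticed at injection and appear only in the records. Side-specific reactions are the safety data that can separate the new formulation from the lidocaine control, and with at most 30 subjects one misclassified subject is visible in the table.

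**Working it through.** **Inputs.** The maximum is 30 subjects (Protocol 4.2.1), hence 30 planned sides per device. The documents give no rate of side exchange, partial treatment or AEs, so the event counts and numbers of affected subjects below are illustrative assumptions. There is no planned safety figure to reproduce. The basis for the sample size is redacted, and the point does not depend on it.

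**Case 1: devices exchanged between sides.** Let A and B be the two devices. Consider a subject with an event on the side injected with A and none on the other. Grouping by allocation takes 1/30 = 3.3 points from A and adds 1/30 to B. The difference A − B moves by 2/30 = 6.7 points, and both denominators stay at 30. If the subject has an event on both sides or on neither, nothing moves. Suppose the true result is 3/30 against 0/30 and every exchanged subject had an event on the A side only (exact 95% intervals in brackets):

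| Exchanged subjects | Reported for A | Reported for B | A − B |
|---|---|---|---|
| 0 | 3/30 = 10.0% (2.1 to 26.5) | 0/30 = 0.0% (0.0 to 11.6) | +10.0 |
| 1 | 2/30 = 6.7% (0.8 to 22.1) | 1/30 = 3.3% (0.1 to 17.2) | +3.3 |
| 2 | 1/30 = 3.3% (0.1 to 17.2) | 2/30 = 6.7% (0.8 to 22.1) | −3.3 |
| 3 | 0/30 = 0.0% (0.0 to 11.6) | 3/30 = 10.0% (2.1 to 26.5) | −10.0 |

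**Case 2: one device never given.** With x events and one unexposed side, the rate by allocation is x/30 and by device received x/29. The understatement is x/29 − x/30 = x/870.

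| x | By allocation | By device received | Understatement (points) |
|---|---|---|---|
| 3 | 3/30 = 10.0% | 3/29 = 10.3% | 0.3 |
| 15 | 15/30 = 50.0% | 15/29 = 51.7% | 1.7 |
| 27 | 27/30 = 90.0% | 27/29 = 93.1% | 3.1 |

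The range for one such subject is 0 to about 3 points. The side was not injected, so there is essentially no local event to misplace.

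**What does not move.** If only the order is wrong, each side still receives its allocated device and no local event changes column. An overall AE incidence counted per subject is the same under either grouping. SAP 6.8 plans exact intervals for overall AE and SAE incidence; the readable text does not say whether that is per subject or per device.

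**The case against.** The strongest objection is the redaction. A rule for analysing safety by device received normally sits in the safety-population definition. SAP 6.4.3 and its protocol counterpart cannot be read, and part of 6.6 is also blacked out. A reader might infer that the plan has no such rule. The documents do not support that, because text hidden by redaction is not absent from the plan. A specific definition in 6.4.3 would also ordinarily govern over one line under general considerations. And 6.6 speaks of treatment group in its preceding listing rule, so allocation may simply be loose wording for device.

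This makes the point conditional but does not remove it. The readable sentence names safety expressly and uses the term that Protocol section 6 uses for the randomised assignment. If 6.4.3 is silent, 6.6 is the operative rule. If 6.4.3 classifies by device received, the two sections need to agree.

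A reader might also infer that either departure misplaces both events and denominators. Neither does: an exchange of sides moves events only, and a single-device subject affects the denominator only. Both would go wrong together only in something like one device being injected on both sides.

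The size is also fairly challenged. Both upper quadrants are injected at the same visit, so partial treatment may be rare, and its basis here is an optional plural in a general withdrawal rule. A 1.7-point change is small beside the exact interval for 15/30, which is 31.3% to 68.7%. The 6.7-point shift needs an exchange in a subject with a one-sided event. The readable safety analysis is descriptive, with no between-device test. All of this stands, and it keeps the point minor.

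**Conclusion.** The point holds conditionally. As readable, SAP 6.6 groups safety by the randomised assignment, which is the wrong basis for side-specific CTRs and local AEs whenever the device injected differs from the device allocated. With 30 subjects:

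- one subject with exchanged sides and a one-sided event shifts the between-device difference by 6.7 points;
- one subject given a single device understates the other device's rate by 0 to about 3 points.

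This assumes that allocation means the randomised side, that no redacted text already overrides 6.6 for safety, and that at least one such case occurs. If none occurs, the effect is nil. The readable text also does not state that the CTR diary is completed separately for each side, although a summary by device in a split-face trial needs it to be.

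The documents do not support a conclusion that the reported safety results will be wrong, or that the primary pain analysis is affected. This is a minor point and a cheap improvement.

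**What to change.** Replace the sentence in SAP 6.6 with:

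*Efficacy data will be summarised by treatment allocation. Side-specific safety data (CTRs and local AEs) will be summarised by the device actually injected in each side, with the number of subjects who received that device as denominator.*

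Align SAP 6.4.3 and 6.8 with it. If 6.4.3 already classifies by device received, make 6.6 cross-refer to it. Settle the wording before unblinding, when Protocol 11.4 requires the populations to be fixed.

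The cost is one derived variable per side for the device actually injected. The records exist: batch numbers and administered volumes (Protocol 7.4), and volumes by quadrant (Protocol 9.3.2.5). The primary analysis is unchanged.

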6.7 Effectiveness Analysis

6.7.1 Primary Endpoint

Effectiveness of RHA[®] [REDACTED] with [REDACTED] versus control will first be analyzed in a non-inferiority statistical model using the pain felt by the subject during injection. If non-inferiority is achieved, pain felt by the subject during injection will be tested for superiority (i.e., to confirm if RHA[®] [REDACTED] is superior to RHA[®] [REDACTED] for reducing pain).

[REDACTED]

signed-rank test

Wilcoxon

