Exclusion Criteria	
 1. Female subjects who are pregnant, breast-feeding, or of childbearing potential and not practicing reliable birth control. 2. Known hypersensitivity or previous allergic reaction to any component of the study devices. 3. [REDACTED] 4. Known sensitivity to local anesthetics of the amide type, history of multiple severe allergies, or history of anaphylactic shock. 
[REDACTED]
 
[REDACTED]
 
 7. History of active chronic debilitating systemic disease that, in the opinion of the investigator, would make the subject a poor candidate in the study. 8. History of connective tissue disease. 9. Malignancy (excluding non-melanoma skin cancer) within the past 5 years.

	
10. Need for clinically significant (TI discretion) and continuous medical treatment within 2 weeks prior to Visit 1.
 
[REDACTED]
 
13. History of skin cancer in the treatment area.
 
14. Elective, clinically significant facial procedures that may confound the interpretation of the results in the perioral region (TI discretion), prior to study enrollment.
 
15. Clinically active disease or infection in the perioral area or mouth (e.g., dental abscess).
 
[REDACTED]
 
17. Medical or psychiatric conditions that may increase the risk associated with study participation or with the interpretation of study results or compliance of the subject and, in the judgment of the Investigator, would make the subject inappropriate for entry into this study.
 
[REDACTED]
 
20. Exposure to any other investigational drug/device within 90 days of entering the study.
 
21. Clinically significant alcohol or drug abuse, or history of poor cooperation or unreliability.

Device Administration
	
[REDACTED]
 
[REDACTED]
 
Injection area: For the purposes of this study, the lip will be defined as the structures within the vermilion border. The focus of this study is to treat perioral rhytids, [REDACTED]
 
[REDACTED]
 
[REDACTED]
 
[REDACTED]

Blinding
	
This is a double-blinded study. Subjects and TI will be blinded to treatment allocation.

Randomization
	
A randomization algorithm will provide equal balancing for the side of the mouth and the order of injection of study devices [REDACTED]

Visit Procedures
	
Refer to the Study Summary Tables and the Study Schematic for a schedule of activities.

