2. OVERVIEW OF STUDY DESIGN

2.1 Study Design

This is a randomized, controlled, double-blinded, within-subject (split-face), multicenter, prospective study to investigate whether RHA[®] [REDACTED] with [REDACTED] is non-inferior to RHA[®] [REDACTED] with lidocaine in terms of injection site pain felt by the subject during injection.

At screening, the Treating Investigator (TI) will evaluate subjects' perioral rhytid severity (using the Perioral Rhytid Severity Rating Scale; PR-SRS) to confirm eligibility and to establish a pre-treatment score for assessing aesthetic improvement.

At Visit 1, RHA[®] [REDACTED] with [REDACTED] will be administered in a random sequence (first or second injection) and side of the mouth and RHA[®] [REDACTED] with lidocaine will be administered to the other side. Study subjects and the TI injecting study devices will be blinded.

[REDACTED]

[REDACTED]

[REDACTED]

Immediately after injection of an upper perioral quadrant, subjects will rate injection site pain experienced **during injection** using a 100 mm Visual Analog Scale (VAS). Injection site pain in each side of the mouth will also be assessed at 15, 30, 45 and 60 minutes after the upper quadrant was injected.

[REDACTED]

Safety evaluation will consist of AE assessments, [REDACTED] [REDACTED] a 30-day CTR diary, and a follow-up call performed by the study site at 72 hours after injection.

Subjects will attend Visit 2 (30 days post-injection) during which efficacy and safety assessments will be conducted. Subjects who present with an unresolved clinically significant device related AE at Visit 2 will receive the optional follow-up phone call no later than 30 days after Visit 2. If the clinically significant AE remains unresolved, the Investigator will request that the subject attend the optional in-clinic follow-up visit (i.e., Visit 3) within 5 working days. Follow-up of the clinically significant AE will continue until the AE is resolved or the TI determines that additional follow-up is not necessary.

[REDACTED]

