6.7.2 Secondary Endpoints

[REDACTED]

Wilcoxon signed-rank test

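### Does the primary pain comparison lose power by leaving injection order and side out of the analysis?

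*SAP*

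**What the plan says.** SAP section 2.1 describes a "randomized, controlled, double-blinded, within-subject (split-face), multicenter, prospective study". Each subject gives one VAS rating immediately after each upper quadrant is injected, so the primary endpoint is one paired difference per subject. The protocol (section 4.2.1) caps the trial at 30 subjects.

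SAP section 3 states that "subjects will be randomized for the side of mouth and the order of injection of study devices". The Randomization row of the protocol synopsis adds: "A randomization algorithm will provide equal balancing for the side of the mouth and the order of injection of study devices".

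On the analysis, SAP section 6.7.1 says that effectiveness "will first be analyzed in a non-inferiority statistical model using the pain felt by the subject during injection", and that superiority is tested if non-inferiority is achieved. A redacted block follows. After it stand two loose fragments, "signed-rank test" and, on a separate line, the name Wilcoxon. Section 6.7.2 is redacted except for "Wilcoxon signed-rank test". Appendix A keeps test names in some of its tables, but the row labels beside them are blacked out.

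**The concern.** The trial randomises and balances injection order, which suggests that its designers thought order could affect pain. The second injection may hurt more or less than the first through anticipation or sensitisation, or because the subject anchors on the first rating. The only efficacy test whose name can be read is the signed-rank test, which has no place for an order or side term. If it is applied to the plain test-minus-control differences, an order effect shifts half the differences up and half down, and the test counts that spread as random error.

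With at most 30 pairs carrying both the non-inferiority test and the superiority test after it, wasted precision would matter. Both factors are known from the randomisation, so adjusting for them would be cheap.

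**Working it through.** **1. What the text can establish.** The concern needs two facts: that the signed-rank test is the primary analysis, and that order and side are absent from it.

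| Needed fact | What is readable | Established? |
|---|---|---|
| Signed-rank is the primary test | Detached words after a redacted block in SAP 6.7.1, with no verb, population or role | No. It could be the main test, a fallback for non-normal data or a sensitivity analysis |
| Order and side are omitted | The readable description is a non-inferiority model; its terms are redacted | No |
| Appendix A ties the test to the primary endpoint | Row labels are redacted, and the first tables show no test name | No |

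The sample size of 30 cannot be reproduced, because its margin, SD, alpha and power are redacted.

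**2. The mechanism, supposing the test were primary and unadjusted.** Let δ be the true test-minus-control difference, π the second-minus-first pain effect, and SD the standard deviation of the difference within an order group. With 15 subjects per order, the difference is centred on δ + π in one group and δ − π in the other. Then

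Var(D) = SD² + π², inflation = 1 + π²/SD², effective n = 30 / inflation.

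With SD = 20 mm (assumed):
- π = 5: 1 + 25/400 = 1.06, effective n = 28.2
- π = 10: 1 + 100/400 = 1.25, effective n = 24.0
- π = 15: 1 + 225/400 = 1.56, effective n = 19.2

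**3. Power.** Assumptions, none of them from the documents: margin 10 mm, δ = 0, one-sided 0.025, no dropout, Normal errors, 20,000 simulated trials per setting. The adjusted column is a linear model of the difference with an order term; it gives the range over the same four values of π.

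| SD (mm) | Signed-rank, π = 0 | π = 5 | π = 10 | π = 15 | Order-adjusted model |
|---|---|---|---|---|---|
| 15 | 93.1% | 91.2% | 84.5% | 70.7% | 93.8–94.0% |
| 20 | 73.2% | 71.6% | 65.1% | 52.7% | 75.0–75.6% |
| 25 | 54.0% | 52.2% | 47.6% | 39.9% | 55.5–55.9% |

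At 5 mm the signed-rank test loses 1.6 to 1.9 points against its own power with no order effect. At SD 20 it loses 73.2 − 65.1 = 8.1 points at 10 mm and 73.2 − 52.7 = 20.5 points at 15 mm. Part of the gap to the adjusted model is not about order. With π = 0 and SD 20, an unadjusted paired t test already has 75.3% against 73.2%, because Normal errors favour it over ranks.

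**4. Type I error.** With the true difference set at the margin and SD 20 (100,000 trials), the unadjusted signed-rank test rejects in 2.49%, 2.17%, 1.45% and 0.66% of trials at π = 0, 5, 10 and 15 mm. The rate falls below the nominal 2.5% as the order effect grows.

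**5. Imbalance.** Bias from unequal order groups is π(n₁ − n₂)/n. For a 16/14 split and π = 10 mm it is 10 × 2/30 = 0.67 mm. Both primary ratings are taken at Visit 1, so later dropout cannot create such a split.

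**The case for a change.** The best case for the concern is that the signed-rank test is the only efficacy test named in the readable text of either document. It appears in SAP 6.7.1, SAP 6.7.2, Appendix A and a remnant in the protocol's statistical section. No readable sentence mentions an order or side term. Both upper quadrants are injected before any lower one, so each primary rating is cleanly a first or a second, and an order effect is plausible. The variance argument is correct, and the simulated power of the adjusted model shows no cost when order has no effect.

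The variance argument stands, and so does the reasonableness of asking the sponsor whether order and side are in the primary model. The inference from readable to complete does not. Where the specification is blacked out, the absence of a term from what remains shows nothing about the plan. The word model does not prove that order is included, but it fits an adjusted analysis at least as well as a bare rank test. An adjusted primary model with the signed-rank test in support may be exactly what the redacted text specifies.

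The claim that adjustment costs nothing was checked only with Normal errors. A VAS bounded at 0 and 100 may be skewed, so a rank method is defensible here.

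**Conclusion.** The concern does not hold. The documents do not show that the signed-rank test is the primary analysis, nor that order and side are left out of it; redaction hides the text that would say. Even on the unproven reading, balanced allocation confines the consequence to lost precision. There is no bias, and the type I error falls below its nominal level, so a false claim of non-inferiority becomes less likely.

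The size of any loss depends on an assumed margin, SD and order effect. It is about 2 points of power at 5 mm and becomes material only from about 10 mm. No readable passage suggests an effect of that size. What is left is a question of clarification to the sponsor, not an error in the plan.
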